2.32 Assess preliminary evaluation of FGFR2 pathway perturbation with ponatinib

2.33 To describe patient-reported health-related quality of life and symptoms

3.0 Patient Eligibility

3.1 Inclusion Criteria

3.11 Age \geq 18 years

3.12 Histological/cytological confirmation of biliary cancer.

3.13 Confirmation of advanced biliary cancer that is refractory or intolerant to gemcitabine or fluoropyrimidine based therapy with FGFR2 fusion [using Next-Gen sequencing assays (such as Foundation One®) or fluorescent in situ hybridization (FISH) break-apart assays] or FGFR pathway mutation/amplification [using Next-Gen sequencing assays (such as Foundation One®)]. Assays must be performed in a CLIA certified laboratory and done as a CLIA validated test or RUO in a CLIA laboratory.

3.14 Measurable disease as defined in Section 11.0.

3.15 ECOG Performance Status (PS) 0, 1 or 2 (Appendix I).

- 3.16 The following laboratory values obtained ≤ 14 days prior to registration.
- Absolute neutrophil count (ANC) $\geq 1500/\text{mm}^3$
 - Platelet count $\geq 100,000/\text{mm}^3$
 - Hemoglobin ≥ 9.0 g/dL
 - Total bilirubin ≤ 1.5 x upper limit of normal (ULN), unless due to Gilbert's syndrome
 - Aspartate transaminase (AST) and Alanine Aminotransferase (ALT) < 3 x ULN
 - Creatinine ≤ 1.5 x upper limit of normal (ULN)
 - Serum lipase and amylase ≤ 2.5 x upper limit of normal (ULN). Note: If subject has tumor involvement in the liver ≤ 3 x ULN.
- 3.17 Negative pregnancy test done ≤ 7 days prior to registration, for women of childbearing potential only.
- 3.18 Recovered from prior radiotherapy and/or systemic therapy related toxicities to Grade ≤ 1
- 3.19a Provide informed written consent.
- 3.19b Life expectancy ≥ 3 months
- 3.19c Willing to return to enrolling institution for follow-up (during the Active Monitoring Phase of the study).
- Note: During the **Active Monitoring** Phase of a study (i.e., active treatment and observation), participants must be willing to return to the consenting institution for follow-up.*
- 3.19d Female and male patients who are fertile agree to use an effective form of contraception with their sexual partners from registration through 4 months after the end of treatment.
- 3.19e Ability to complete questionnaire(s) by themselves or with assistance.

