4.0 Test Schedule

Cycle = 28 days

Tests and procedures	Active Monitoring Phase						
	≤14 days prior to registration	Cycle 1 Day 1 (± 2 days) prior to treatment	Cycle 1 Days 8, 15, 22 prior to treatment	Cycle 2 and beyond Day 1 (± 2 days) prior to treatment	Q 8 weeks from Cycle 1 Day 1 (± 5 days)	Every 3 Cycles starting at end of Cycle 3 (± 5 days)	End of treatment
History and exam, wt, ECOG	X			X			X
Height, Child Pugh score	X						
Vitals ³	X	X	X	X			X
Hematology group WBC, ANC, Hgb, PLT	X	X	X	X			X
Chemistry group Sodium, potassium, chloride, bicarbonate, total protein, albumin, calcium, glucose, BUN, total bilirubin, creatinine, alkaline phosphatase, SGOT (AST), SGPT (ALT)	X	X		X			X
Amylase ^R	X	X	X	X			
Lipase ^R	X	X	X	X			
CA19-9		X		X ⁵			
EKG ^R	X					X	
Echocardiogram	X			X ¹⁰			
Tumor measurement and Imaging (CT or MRI as clinically)	X ¹				X ²		

indicated)							
Pregnancy test	X ⁴						
Patient questionnaire booklet	X ⁹			X ⁹			
Adverse event assessment	X		X	X			
Research Archival Tissue (optional)	X ⁸						
Research Tissue Biopsy (optional)				X ^{7,R}			X ⁶
Research blood samples (Optional)	X			X			X

1. Imaging studies such as CT scans, and MRIs can be performed ≤ 28 days prior to registration. Use same imaging throughout the study. Assessment by physical exam should be done ≤ 14 days prior to registration.
 2. Tumor assessment must be performed at least every 8 weeks. Tumor assessment should be performed at any time during the treatment cycle that disease progression is clinically suspected so that patient can go off treatment and receive other therapy.
 3. Includes weight, blood pressure, pulse and temperature
 4. Women of childbearing potential only. Must be done ≤ 7 days prior to registration.
 5. Only to be collected if $> \text{ULN}$ on Cycle 1 Day 1
 6. If patient has experienced disease progression and at such time a standard of care biopsy is ordered by the treating physician, waste specimen will be collected, fresh frozen and stored for future correlative studies. Perform only if archival specimen was available.
 7. Perform only if archival specimen was available.
 8. Archival FFPE and/or fresh frozen tissue collected in setting of standard of care procedures.
 9. Patient questionnaire booklet must be used; copies are not acceptable for this submission. Booklet should be completed by patient prior to review of treatment response and discussions of patient's general health since last treatment evaluation.

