11.44 Overall Objective Status

The overall objective status for an evaluation is determined by combining the patient's status on target lesions, target lymph nodes, non-target lesions, non-target lymph nodes, and new disease as defined in the following tables:

For Patients with Measurable Disease

Target Lesions & Target Lymph Nodes	Non-Target Lesions & Non-Target Lymph Nodes	New Sites of Disease	Overall Objective Status
CR	CR	No	CR
CR	Non-CR/Non-PD	No	PR
PR	CR	No	PR
	Non-CR/Non-PD		
CR/PR	Not All Evaluated*	No	PR**
SD	CR	No	SD
	Non-CR/Non-PD		
	Not All Evaluated*		
Not all Evaluated	CR	No	Not Evaluated (NE)
	Non-CR/Non-PD		
	Not All Evaluated*		
PD	Unequivocal PD	Yes or No	PD
	CR		
	Non-CR/Non-PD		
	Not All Evaluated*		
CR/PR/SD/PD/Not all Evaluated	Unequivocal PD	Yes or No	PD
CR/PR/SD/PD/Not all Evaluated	CR	Yes	PD
	Non-CR/Non-PD		
	Not All Evaluated*		

*See Section 11.431

** NOTE: This study uses the protocol RECIST v1.1 template dated 2/16/2011. For data collection and analysis purposes the objective status changed from SD to PR in the MCCC protocol RECIST v1.1 template as of 2/16/2011 and to match RECIST v1.1 requirements.

11.45 Symptomatic Deterioration: Patients with global deterioration of health status requiring discontinuation of treatment without objective evidence of disease progression at that time, and not either related to study treatment or other medical conditions, should be reported as PD due to “symptomatic deterioration.” Every effort should be made to document the objective progression even after discontinuation of treatment due to symptomatic deterioration. A patient is classified as having PD due to “symptomatic deterioration” if any of the following occur that are not either related to study treatment or other medical conditions:

- Worsening of tumor-related symptoms.
- Decline in performance status to >3 level on ECOG scale.

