13.0 Treatment/Follow-up Decision at Evaluation of Patient

- 13.1 Patients who are CR, PR, or SD will continue treatment per protocol.
- 13.2 Patients who develop PD while receiving therapy will go to the event monitoring phase.
- 13.3 Patients who go off protocol treatment for reasons other than PD will go to the event monitoring phase per Section 18.0.
- 13.4 A patient is deemed *ineligible* if after registration, it is determined that at the time of registration, the patient did not satisfy each and every eligibility criteria for study entry. The patient may continue treatment off-protocol at the discretion of the physician as long as there are no safety concerns, and the patient was properly registered. The patient will go directly to the event monitoring phase of the study (or off study, if applicable).
- If the patient received treatment, all data up until the point of confirmation of ineligibility must be submitted. Event monitoring will be required per Section 18.0 of the protocol.

- If the patient never received treatment, on-study material and the End of Active Treatment/Cancel Notification Form must be submitted. No further data submission is necessary.
- 13.5 A patient is deemed a *major violation*, if protocol requirements regarding treatment in cycle 1 of the initial therapy are severely violated that evaluability for primary end point is questionable. All data up until the point of confirmation of a major violation must be submitted. The patient will go directly to the event-monitoring phase of the study. The patient may continue treatment off-protocol at the discretion of the physician as long as there are no safety concerns, and the patient was properly registered. Event monitoring will be required per Section 18.0 of the protocol.
- 13.7 A patient is deemed a *cancel* if he/she is removed from the study for any reason before any study treatment is given. On-study material and the End of Active Treatment/Cancel Notification Form must be submitted. No further data submission is necessary.

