
A paper booklet containing all the patient-reported outcomes will be administered in clinic at baseline and every cycle, and each PRO will be scored according to the published scoring algorithm. Scale score trajectories over time will be examined using stream plots and mean plots with standard deviation error bars overall. Changes from baseline at each cycle will be statistically tested using paired t-tests, and standardized response means (mean of the change from

baseline scores at a given cycle, divided by the standard deviation of the change scores) will be interpreted (after applying Middel's (2002) adjustment) using Cohen's (1988) cut-offs: <0.20 = trivial; $0.20-0.50$ = small; $0.50-0.80$ = moderate; and ≥ 0.80 = large. Correlation between outcomes will employ Pearson and/or Spearman correlations at individual time points.

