18.0 Records and Data Collection Procedures

18.1 Submission Timetable

Initial Material(s)

CRF	Active-Monitoring Phase (Compliance with Test Schedule Section 4.0)
On-Study	≤14 days after registration
Adverse Event - Baseline	
RECIST Measurement – Baseline	
Concomitant Medication - Baseline	
Hematology Laboratory	
Chemistry Laboratory	
Other Laboratory	
Patient Questionnaire Booklet ¹	
Booklet Compliance ²	
OP and Path Reports (see Section 17.0)	
Research Blood Submission	≤30 days after registration
Research Tissue Submission	
End of Active Treatment/Cancel Notification	Submit ≤2 weeks after registration if withdrawal/refusal occurs prior to beginning protocol therapy

1. Patient questionnaire booklet **must** be used; copies are not acceptable for this submission.
2. This form must be completed only if the patient questionnaire booklet contains absolutely NO patient provided assessment information.

Test Schedule Material(s)

CRF	Active-Monitoring Phase (Compliance with Test Schedule Section 4.0)
	At each evaluation during treatment
Evaluation/Treatment	X ¹
Adverse Event	X

CRF	Active-Monitoring Phase (Compliance with Test Schedule Section 4.0)
	At each evaluation during treatment
RECIST Measurement	X
Concomitant Medication	X
Other Laboratory	X (see Section 4.0)
Hematology Laboratory	X (see Section 4.0)
Chemistry Laboratory	X (see Section 4.0)
Research Tissue Submission	X (see Section 17.0)
Research Blood Submission	X (see Section 14.0)
Patient Questionnaire Booklet	X ²
Booklet Compliance	X ³
End of Active Treatment/Cancel Notification	X
Notification Form – Grade 4 or 5 Non-AER Reportable Events/Hospitalization	At each occurrence (see Section 10.0)
ADR/AER	At each occurrence (see Section 10.0)

1. Complete at each evaluation during Active Treatment (see Section 4.0).
2. Patient questionnaire booklet **must** be used; copies are not acceptable for this submission. To be completed prior to treatment every cycle.
3. This form must be completed only if the patient questionnaire booklet contains absolutely NO patient provided assessment information.

Follow-up Material(s)

CRF	Event Monitoring Phase ¹				
	q. 6 months until PD	At PD	After PD q. 6 mos.	Death	New Primary
Event Monitoring	X ²	X ²	X	X	At each occurrence

1. If a patient is still alive 2 years after registration, no further follow-up is required.
2. Submit copy of documentation of response or progression to the MCCC Operations Office, Attention: XXXXXXXXXX.

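### The per-cycle paired t-tests of patient-reported outcomes describe only patients still on treatment, and can understate worsening at later cycles if those who worsen stop

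*Combined protocol and SAP*

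**What the plan says.** The objective is Section 2.33, under Translational/Correlative Research: "To describe patient-reported health-related quality of life and symptoms".

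Section 16.34 sets the analysis. "Changes from baseline at each cycle will be statistically tested using paired t-tests". Standardized response means (mean change divided by the SD of change) are interpreted, after Middel's adjustment, with cut-offs at 0.20, 0.50 and 0.80. Stream plots and mean plots are added. The section has no longitudinal model, no missing-data rule and no sensitivity analysis, and it does not promise the number of patients behind each cycle's result.

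On collection, Section 16.34 says: "A paper booklet containing all the patient-reported outcomes will be administered in clinic at baseline and every cycle". The case-report-form timetable in Section 18.1 lists the booklet under the Active-Monitoring Phase only: "To be completed prior to treatment every cycle". The test schedule in Section 4.0 marks it at screening and at Day 1 of Cycle 2 and beyond. The End of treatment cell in that row is empty.

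On leaving treatment, Section 13.2 says: "Patients who develop PD while receiving therapy will go to the event monitoring phase". Section 13.3 adds: "Patients who go off protocol treatment for reasons other than PD will go to the event monitoring phase per Section 18.0". The only form listed for that phase in Section 18.1 is the Event Monitoring form. Section 11.45 also classes as progression: "Patients with global deterioration of health status requiring discontinuation of treatment without objective evidence of disease progression at that time", unless treatment or another condition explains it.

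**The concern.** A paired test at a given cycle can use only patients with a booklet at that cycle. Pairing removes baseline differences between those who stay and those who leave. It does not remove selection on what happened after baseline.

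The protocol links that selection to the outcome being measured. Worsening tumour-related symptoms or performance status can end treatment as progression, and the dose-modification table in Section 8.2 ends treatment for specified toxicities. The questionnaires measure symptom burden and function, so patients with poor trajectories are plausibly the ones who stop providing booklets.

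At stake is the patient-reported tolerability statement. A late-cycle change could be labelled trivial because the patients who felt worse are no longer measured, and nothing in the planned output would alert the reader.

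**Working it through.** **1. The plan's own figures.** Section 16.34 gives no SD, effect size, retention or power. The only design figure to reproduce is the two-stage table in Section 16.24 (10 patients, stop if 0 successes; 27 patients, promising if 3 or more). Exact binomial sums give probabilities of declaring the regimen promising of 0.1204, 0.4324, 0.6980, 0.8541 and 0.9322 at true rates 0.05 to 0.25. Stage 1 stopping probabilities are 0.5987, 0.3487, 0.1969, 0.1074 and 0.0563. All match after rounding. The table does not bear on the patient-reported analysis except through the possible sample sizes, 10 or 27.

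**2. Who is left late on.** Sections 13.1 and 13.2 keep patients with response or stable disease on treatment and move those with progression off it. The primary endpoint counts confirmed response or stable disease for 4 or more cycles. Patients still on treatment after four cycles are therefore largely the clinical-benefit patients. At the plan's null and target rates that is 0.05 × 27 = 1.35 and 0.20 × 27 = 5.4 patients. These are design rates, not forecasts, but they show that late-cycle results may rest on few patients, selected for disease control.

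**3. What drives the bias.** Let r be the fraction still giving booklets at a cycle and D the change from baseline. Since E[D] = r·E[D | on] + (1 − r)·E[D | off], the bias of the on-treatment mean is

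E[D | on] − E[D] = (1 − r)·(E[D | on] − E[D | off]).

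It is zero if leavers and stayers have the same mean change. The documents give neither r nor that difference.

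**4. Illustration.** All inputs are assumptions, in units of the baseline SD: 27 patients; five post-baseline cycles; each patient's true change per cycle drawn from a normal with mean -0.20 and SD 0.25; measurement SD 0.5 on the change score; probability of leaving before each booklet = logistic(base − g × current true change); about 26-29% retained by the fifth cycle. The true change at the fifth cycle is 5 × (-0.20) = -1.00. The true standardized response mean is -1.00 / √((5 × 0.25)² + 0.5²) = -1.00 / 1.346 = -0.74, moderate before Middel's adjustment.

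| Cycle after baseline | True mean | On-treatment mean, g = 1 | On-treatment mean, g = 2 |
|---|---|---|---|
| 1 | -0.20 | -0.19 | -0.18 |
| 2 | -0.40 | -0.32 | -0.27 |
| 3 | -0.60 | -0.36 | -0.21 |
| 4 | -0.80 | -0.29 | -0.04 |
| 5 | -1.00 | -0.11 | +0.18 |

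With g = 0 there is no bias, only loss of numbers (about 21, 16, 12, 9 and 7 of 27). At the fifth cycle the standardized response mean is -0.10 for g = 1 and +0.18 for g = 2, both trivial in size. A two-sided 5% paired test, counted only when it shows worsening, succeeds in 38%, 5% and 1% of trials for g = 0, 1 and 2, against about 96% if all 27 had been measured. As a check on step 3 for g = 1: the bias is -0.11 − (-1.00) = 0.89, and with r about 0.27 stayers and leavers differ by 0.89 / 0.73 = 1.22 SD.

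**5. How far a mixed model helps.** In further simulations with 27 patients and a true change of -12 points (baseline SD 18 and about 40-50% retained, again assumed), Cycle 4 estimates were:

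| Leaving depends on | Paired mean | Mixed model |
|---|---|---|
| Nothing related to scores | about -12 | about -12 |
| Last observed score | -4.7 to -9.5 | -11.6 to -14.0 |
| Current, unobserved status | -0.6 to -4.3 | -4.1 to -7.1 |

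The ranges span several settings of dropout strength. On the scale of step 4, with leaving driven by current true status, the model gave about -0.98, -0.75 and -0.60 for g = 0, 1 and 2 against -1.00. In one run, 15-39% of random-slope fits failed to converge or were singular at 27 patients, and about 30% at 10.

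**The case against.** The goal is descriptive and correlative, the trial is single-arm, and no decision rule uses these scores. An on-treatment mean is a legitimate quantity if it is named as such. This stands, and it caps the point at a cheap improvement. It does not remove the point, because the plan tests and labels each cycle without saying whom the result describes.

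The timing of the booklet also helps: "Booklet should be completed by patient prior to review of treatment response and discussions of patient's general health since last treatment evaluation". A patient whose progression is declared at a cycle visit may thus give one last score. This stands in part. The score enters only that cycle's test, and a patient who stops between visits has no scheduled booklet.

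Three stronger readings are tempting, and the documents do not support them.

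- A reader might infer that these patients leave the study. They leave treatment and booklet collection; Section 18.1 still follows them for progression and survival.
- A reader might infer that leavers' early scores are thrown away. They enter the tests and standardized response means for the cycles they completed, and the plots. They are absent only from later cycles' tests.
- A reader might infer that the bias is certain, or that a mixed model removes it. The bias is zero if leaving is unrelated to scores. Near-full recovery appears only when leaving is predictable from scores already recorded, and one run in that setting overshot to -14.0.

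**Conclusion.** The point holds as a limited one. That later-cycle tests use only patients still on treatment is inferred from the booklet schedule and the rules for leaving; Section 16.34 does not say so. Given that, the means, tests and effect-size labels can understate worsening at later cycles if patients who worsen stop treatment, as Section 11.45 makes plausible.

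The size is unknown. Under the assumed inputs, the error in a true -1.00 SD change runs from nothing to more than the whole change. A mixed model on all collected scores reduced the error whenever leaving depended on scores or status, and cost essentially nothing in bias when it did not. It is a better main analysis, not a full correction. The primary endpoint, the stopping rules and the go/no-go decision are untouched.

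**What to change.** Amend Section 16.34 as follows.

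1. For each scale score, including the single-item Uniscale, make the main analysis one linear mixed model on all observed scores, baseline included, with cycle as a categorical fixed effect.
2. Pre-specify the covariance: random intercept and slope, falling back to random intercept alone if the model does not converge or if the trial stops at 10 patients.
3. Report the model-estimated change at each cycle with a confidence interval and the number of patients contributing.
4. Keep the plots, paired changes and standardized response means (with their labels) as descriptions, explicitly headed on-treatment.
5. State that the model corrects only partly if leaving depends on status that no booklet recorded.

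The cost is a wording change and slightly more analysis, with no new patients or visits. The drawback is possible non-convergence at late cycles or with 10 patients, which the fallback is there to handle. An end-of-treatment booklet would address the unrecorded status more directly, but it changes data collection and is a separate, optional step.

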16.2 Statistical Design

16.21 The largest clinical benefit where the proposed treatment regimen would be considered ineffective in this population is 5%, and the smallest clinical benefit rate that would warrant subsequent studies with the proposed regimen in this patient population is 20%. The following two-stage Simon Optimum design uses 10 or 27 patients to test the null hypothesis that the true clinical benefit rate in a given patient population is at most 5%.

The null clinical benefit rate of 5% is based on response rates observed for refractory solid tumors with single agents in an unselected/empiric setting (Horstmann, E. et al., 2005).

16.211 STAGE 1: Enter 10 patients into the study. If 0 successes (i.e., patients deemed as having clinical benefit) are observed in the first 10 evaluable patients, we will consider this regimen ineffective in this patient population and terminate this study. Otherwise, if the number of successes is at least 1, we will proceed to Stage 2.

16.212 STAGE 2: Enter an additional 17 patients into the study. If 2 or fewer successes are observed in the first 27 evaluable patients, we will consider this regimen ineffective in this patient population. If 3 or more successes are observed in the first 27 evaluable patients, we may recommend further testing of this regimen in subsequent studies in this population.

16.213 NOTE: Accrual will be suspended between stages to allow patients to become evaluable for the primary endpoint.

16.211 Over Accrual: If more than the target number of patients are accrued, the additional patients will not be used to evaluate the stopping rule or used in any decision making process. Analysis involving over accrued patients is discussed in Section 16.313.

16.22 Sample Size: The two-stage study design to be utilized is fully described in Section 16.21. A minimum of 10 and a maximum of 27 evaluable patients accrued onto this study unless undue adverse events are encountered. We anticipate accruing an additional 3 patients to account for ineligibility, cancellation, major treatment violation, or other reasons. Thus, **a maximum of 30 patients will be accrued onto this study** in order to have 27 evaluable patients available for the statistical design described in Section 16.21.

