16.33 Translational Analyses

Rate of FGFR fusions and ctDNA mutations will be described, and association with confirmed tumor response and/or clinical benefit will be investigated using a Fisher's exact test. Given the small sample size, all translational analyses are

considered exploratory and no adjustment for multiplicity will be employed. One-sided p-values ≤ 0.10 are considered statistically significant throughout.

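### Size labels for patient-reported change come from the point estimate, with no interval and no tie to the paired t-test, so at small n they often signal change where there is none

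*Combined protocol and SAP*

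**What the plan says.** Section 16.34 has a booklet of questionnaires that "will be administered in clinic at baseline and every cycle". Two analyses of change are then planned for each cycle.

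- A test: "Changes from baseline at each cycle will be statistically tested using paired t-tests". Section 16.34 gives no significance level and no sidedness for it.
- A size label. The SRM is the mean of the change from "baseline scores at a given cycle, divided by the standard deviation of the change scores". It "will be interpreted (after applying Middel's (2002) adjustment") "using Cohen's (1988) cut-offs: <0.20 = trivial", with small from 0.20, moderate from 0.50 and large from 0.80.

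The section plans no confidence interval for the SRM, sets no minimum number of patients for a label, and does not make the label depend on the test. The mean plots carry standard deviation bars.

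On numbers, section 16.22 gives "A minimum of 10 and a maximum of 27 evaluable patients accrued onto this study" and adds that "a maximum of 30 patients will be accrued onto this study". No count of patients with questionnaire data is given for any cycle. Under section 13.2, patients who progress leave for event monitoring.

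**The concern.** An SRM from n patients has a standard error of about 1/√n when there is no true change. That is 0.19 at n=27, 0.29 at n=12 and 0.45 at n=5. At the smaller sizes the error exceeds the 0.20 boundary between trivial and small and approaches the 0.50 boundary for moderate. A label read straight from the estimate then reflects sampling error to a large extent. This would be so even if no patient dropped out selectively.

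Goal 2.33 is to describe patient-reported quality of life and symptoms, and several multi-scale instruments are graded at every cycle. Without an interval, a reader of the tables cannot see from the label whether a small or moderate change is well supported. Equally, a trivial label at small n could be taken as showing that nothing changed.

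**Working it through.** **The plan's own figures.** Section 16.34 states no precision or power. The benefit rates used below to gauge later-cycle numbers come from the two-stage design, so I checked that table first. The stage 1 stopping probability is (1−p)^10: 0.95^10 = 0.599 and 0.80^10 = 0.107, against 0.60 and 0.11 in section 16.24. The probability of declaring the regimen worth further study is the sum over x ≥ 1 of P(X1 = x) × P(X2 ≥ 3−x), with X1 ~ Bin(10, p) and X2 ~ Bin(17, p). It is 0.120 at p = 0.05 and 0.854 at p = 0.20, against 0.12 and 0.85. The table reproduces.

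**Label probability with no true change.** By the definition in section 16.34, SRM = t/√n, where t is the paired t statistic. With normal change scores and no true change, √n × SRM follows a t distribution with n−1 degrees of freedom, so the chance that the absolute SRM reaches a cut-off c is 2 × P(T > c√n). For c = 0.20 at n=12, c√n = 0.693 on 11 df, giving 0.503. The fourth column below is t(0.975, n−1)/√n. The last column is the second minus 5 points, because at these n the significant results all lie above the 0.20 cut-off.

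| n | small or larger | moderate or larger | absolute SRM needed for two-sided p ≤ 0.05 | small or larger but not significant |
|---|---|---|---|---|
| 27 | 30.8% | 1.5% | 0.396 | 26% |
| 12 | 50.3% | 11.1% | 0.635 | 45% |
| 10 | 54.3% | 14.8% | 0.715 | 49% |
| 5 | 67.8% | 32.6% | 1.242 | 63% |

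These count both directions. Worsening alone is half of each figure, for example about 25% at n=12. Simulation with 200,000 runs gave 50.4% at n=12 and 30.9% at n=27 for small or larger.

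**Effect of the adjustment.** The table applies if the adjustment leaves the SRM unchanged. As an assumption, let it multiply the SRM by √(2(1−r)), with r the correlation between baseline and follow-up. The 0.20 cut-off then corresponds to 0.20/√(2(1−r)) on the unadjusted SRM.

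| r | equivalent cut-off | n=27 | n=12 | n=5 |
|---|---|---|---|---|
| 0.3 | 0.169 | 38.8% | 57.0% | 72.5% |
| 0.5 | 0.200 | 30.8% | 50.3% | 67.8% |
| 0.7 | 0.258 | 19.1% | 39.0% | 59.5% |
| 0.8 | 0.316 | 11.2% | 29.7% | 52% |

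**Later-cycle n.** Clinical benefit is a confirmed response, or stable disease for 4 or more cycles (section 16.11). If the patients with benefit roughly match those still giving data after cycle 4, the 20% target rate gives 27 × 0.20 = 5.4. At 25%, the highest rate tabulated, 27 × 0.25 = 6.75, and the binomial chance of 12 or fewer is 0.992. If the study stops at Stage 1 with 10 evaluable patients, n is about 10 or fewer at every cycle.

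**The case against.** The strongest reply is that the label does not stand alone. The same sentence plans a paired t-test, which is the tool for separating change from no change. Because SRM = t/√n, a reader given the test result and n can recover the precision. The section also plans stream plots, mean plots and correlations, the goal is descriptive, and no decision rule uses it.

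Much of that stands. A reader might infer that the plan has no means of telling change from no change, or that goal 2.33 is reported only through labels. The documents support neither. What remains is that the label is not tied to the test. Section 16.34 gives no level for the test, and the only one nearby, "One-sided p-values ≤ 0.10 are considered statistically significant throughout", sits in the translational section, with no statement that it covers the questionnaires. Even if it did, one-sided significance would need an SRM of t(0.90, n−1)/√n, which is 0.39 at n=12 and 0.69 at n=5, well above the 0.20 at which a change is called small. The plotted SD bars do not narrow with n, so they do not show precision either.

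Two further objections limit the size of the point. First, a figure of about half at n=12 depends on the adjustment: at r = 0.7 under the assumed form it is 39%, and half is reached only at n of 7 or fewer. Second, small n is inferred. For a study that reaches Stage 2, nothing in the documents puts n at 12 or fewer in cycles 2 to 4.

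**Conclusion.** The point holds as a reporting weakness. The plan attaches size labels to point estimates whose error, at the n this design implies after cycle 4, is as wide as the label categories. Under no true change, a label of small or larger is expected about 31% of the time at n=27, 50% at n=12 and 68% at n=5 if the adjustment has no effect. For r from 0.7 to 0.3 under the assumed factor, the ranges are 39–57% at n=12 and 59–72% at n=5. These rest on normal change scores, cut-offs applied in either direction, an assumed adjustment formula, and the benefit rate as a guide to who remains.

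A reader might go on to infer that most small changes reported at later cycles would be noise. That does not follow. The calculation gives the chance of a label when nothing has changed. The share of labels that are noise also depends on how many scales truly change, which the documents do not give. Section 15.17 lists rash, diarrhea, nausea and fatigue in more than 10% of patients, so no change on every scale is not a safe default. The matter is minor, because neither the primary endpoint nor the stopping rules use these labels.

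**What to change.** Add to section 16.34, in words such as: *Each adjusted standardized response mean will be reported with the number of patients contributing and its 95% confidence interval, beside the paired t-test. The Cohen label describes the point estimate only and is to be read against the interval. When the interval includes 0, the label will not be reported as evidence of change, and a label of trivial will not be reported as evidence of no change.* The interval should pass through the same adjustment as the estimate, so the formula used should be stated there.

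A stricter rule is tempting: give a size label only when the interval excludes 0, and trivial only when the whole interval lies within ±0.20. It would not work here. Even for an estimate of exactly 0, the second condition needs t(0.975, n−1)/√n to fall to 0.20, which takes n of about 99 against a cap of 30. The first needs an unadjusted SRM of at least 0.514 at n=17, so small could never be assigned at n of 17 or fewer, and the labels that survived would tend to be exaggerated.

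The cost is the added text and a table column for n and the interval, with no new data. The downside is that many later-cycle labels will visibly be imprecise.
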